**Table 1: Dosage regimen**

Daily dose	
Dose A	50 mg (half a tablet of 100 mg)
Dose B	100 mg (one tablet of 100 mg)
Dose C	150 mg (one and a half tablet of 100 mg)
Dose D	200 mg (two tablets of 100 mg)

Each next dose will start after 14 days of treatment if the previous dose was considered safe by the investigator. The up-titration is based on the following safety criteria, including but not limited to:

- Absence of symptomatic and/or clinically relevant orthostatic hypotension
- SBP > 95 mmHg or DBP > 50 mmHg
- Absence of clinically significant changes in ECG parameters (heart rate, P-R interval, QRS duration, QT and QTc interval)
- Absence of clinically significant hypersensitivity/skin allergic reactions

Patients not fulfilling the criteria for up-titration after 14 days of treatment with 50 mg zamicastat have to be withdrawn from the study.

If the patient's next dose will not be tolerated by the patient, the dose has to be down-titrated to his/her previous dose and this dose will be considered as the individual HTD, if tolerated by the patient. Treatment at the individual HTD will be for 42 days during the maintenance period.

Zamicastat has to be taken in the morning after breakfast. The patient must not take the tablet at home on visit days (A3/B3/C3/D3, MPV1, MPV2 and MPV3).

Patients taking 150 mg or 200 mg of zamicastat and who will not participate in the extension study will take 100 mg zamicastat for 14 days.

In case a patient will discontinue the study early due to the occurrence of an AE, down-titration is not mandatory, but at the investigator's discretion.

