### Dose finding period

The dose finding period will be defined as the period from the date of the first IMP intake to the day before visit D3 or the day before IMP down-titration.

The dose finding period will be split into **dose toleration periods** for each dose prescribed for that period. The period will start from the date of the IMP taken at the site at visit A1/A3/B3/C3 to the day before visit A3/B3/C3/D3 or the day before IMP down-titration.

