### Maintenance period

The maintenance period will be defined as the period between visit D3 or the date of IMP down-titration and the date of the last IMP intake until MPV3 (including the first day of visit). For patients participating in the extension study, the end of the maintenance period will be the end date of visit MPV3.

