Adverse events will be assigned to IMP dose groups based on the prescribed IMP dose at the date of AE onset. AEs with an onset date on the same day as a down-titration will be assigned to the previous dose. If the AE onset date is incomplete such that it could belong to more than one prescribed dose, the AE will be assigned to all such doses.

The following statistical output will be provided:

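### Adverse events starting on the day of down-titration are counted in the maintenance period at a dose the patient did not take in maintenance

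*SAP*

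**What the plan says.** Four parts of the SAP meet on the down-titration date.

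- **End of dose finding (SAP 4.6).** The period runs "to the day before visit D3 or the day before IMP down-titration". The dose toleration periods within it stop in the same way: "to the day before visit A3/B3/C3/D3 or the day before IMP down-titration".
- **Start of maintenance (SAP 4.6).** "The maintenance period will be defined as the period between visit D3 or the date of IMP down-titration". The down-titration date is thus the first maintenance day.
- **Dose for an adverse event (SAP 5.6.1).** The default is: "Adverse events will be assigned to IMP dose groups based on the prescribed IMP dose at the date of AE onset". The exception follows: "AEs with an onset date on the same day as a down-titration will be assigned to the previous dose". Nothing comparable is said about period.
- **Tables (SAP 5.6.1).** Tables 15.3.1.1 to 15.3.1.9 report treatment-emergent events for the whole trial and separately for dose finding, maintenance and the final down-titration period, by concurrent dose. Percentages use the safety set.

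Two further statements matter. SAP 2.3 makes the maintenance dose the individual highest tolerated dose (HTD) and has patients who cannot tolerate it in maintenance leave the study. SAP 2.5 uses *previous dose* for the lower dose returned to: "the dose has to be down-titrated to his/her previous dose and this dose will be considered as the individual HTD". Footnote 9 of the SAP 1.2 schedule uses it in the same sense.

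**The concern.** The SAP recognises that the down-titration day is awkward for dose and writes a rule for it, but does not carry that rule over to period. The two classifications then disagree for the same event in the same table.

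The events exposed to this include those that end dose finding. SAP 2.3 asks patients who do not tolerate a dose to come in or call at once. Footnote 19 of the SAP 1.2 schedule also allows down-titration at a scheduled visit, and protocol 12.2 counts clinically significant observations made at a visit as adverse events. Onset and down-titration can therefore share a date.

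Table 15.3.1.7 (events leading to down-titration) shows the effect most clearly. Because intolerance of the HTD in maintenance leads to withdrawal, its maintenance column should normally be empty. Under the present rules a triggering event with same-day onset appears there, and could be read as intolerance of the maintenance dose. Tolerability of the different doses is a secondary objective, so the layout of these tables matters.

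**Working it through.** The plan gives no figure to reproduce. The check applies the SAP's date rules to one assumed patient: 50 mg from day 1, 100 mg from day 15, 150 mg from day 29, reduced to 100 mg on day 34. The HTD is then 100 mg.

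**Period (SAP 4.6).** Dose finding covers day 1 to day 34 − 1 = 33. Maintenance day number = day − 34 + 1, so day 34 is maintenance day 1 and day 35 is maintenance day 2.

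**Dose (SAP 5.6.1).** The default is the prescribed dose on the onset date; on day 34 the exception applies.

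| Onset | Period | Dose, if *previous* means the dose before the reduction | Dose, if *previous* has the SAP 2.5 sense |
|---|---|---|---|
| Day 33 | Dose finding | 150 mg | 150 mg |
| Day 34 | Maintenance, day 1 | 150 mg | 100 mg |
| Day 35 | Maintenance, day 2 | 100 mg | 100 mg |

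The day-34 event falls in maintenance under either reading. Under the first, and more natural, reading it is shown in maintenance at 150 mg, although this patient's maintenance dose is 100 mg.

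**Is this overridden elsewhere?** SAP 4.3 refers dose assignment to 5.6.1. No section gives a separate rule for placing adverse events in periods.

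**Size.** The denominator is the safety set; 32 is the planned number of patients (SAP 2.6). For *k* affected patients, the largest shift between the two period columns is 100 × *k*/32:

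- *k* = 1: 3.1 percentage points
- *k* = 3: 9.4 percentage points
- *k* = 5: 15.6 percentage points

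The values of *k* are illustrative. Each shift is a maximum, because a patient who also has an event in the same row during dose finding stays counted there.

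**After the fix.** The day-34 event moves to dose finding at 150 mg, and period and dose agree.

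**The case against.** The strongest reply is that the effect is narrow. Only events with onset on the exact down-titration date are touched; a dose-limiting event that began earlier stays in dose finding at the right dose. Whole-trial totals are unchanged, and Tables 15.3.1.10 and 15.3.1.11 have no stated period split. No event leaves Table 15.3.1.7, since membership depends on the recorded action of dose reduction; only its period column changes. The HTD does not depend on these tables, the listings show start dates, and the study is descriptive. All of this stands and limits the importance of the point. It does not remove the mismatch.

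A reader might go further and infer two things that the documents do not support.

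*That the event is credited to the wrong dose.* SAP 2.5 and footnote 9 do use *previous dose* for the lower dose. But the sentence in 5.6.1 is an exception to the prescribed-dose default, and as an exception it naturally means the dose before the reduction. SAP 2.5 also uses the term for the dose in use just before an increase. This is an ambiguity worth removing, not a demonstrated misassignment.

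*That same-day onset is common and several dose-limiting events are misplaced.* Prompt contact once a dose is not tolerated is not the same as contact on the day symptoms begin. The documents give neither a down-titration rate nor a same-day share, so any count would only restate an assumption. The SAP also does not say whether the recorded down-titration date is the day of the decision or of the first lower intake; if the latter, coincidence could be uncommon. The number affected could be zero.

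**Conclusion.** The period mismatch is real and follows directly from SAP 4.6 and 5.6.1 read together. In Tables 15.3.1.1 to 15.3.1.9, an event starting on the down-titration day is shown in maintenance at a dose the patient did not take in maintenance, and is missing from dose finding. This assumes that *previous dose* in 5.6.1 means the pre-reduction dose. If it were read as the lower dose, the period would still be maintenance and the event would also sit at the tolerated dose.

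The size is up to 3.1 percentage points per affected patient between two period columns, assuming a safety set of 32. The number of affected patients is unknown. Importance is minor to moderate: the effect is confined to the period columns, but it can reach events that end dose finding, and it is easily avoided. The table shells were not among the documents, so a clarifying note there cannot be ruled out.

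**What to change.** Replace the same-day sentence in SAP 5.6.1 with wording such as: *For down-titrations during the dose finding period, adverse events with onset on the date of down-titration are assigned to the dose prescribed immediately before the down-titration and to the dose finding period.* In the same edit, state whether that date is the day of the decision or of the first intake at the lower dose.

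The limitation to dose finding matters because eligible patients also step down after MPV3, and those events should not be moved into dose finding; keep a separate statement of the dose rule for them. Placing the rule in 5.6.1 leaves the period definitions in 4.6, and the exposure and compliance calculations that use them, as they are.

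The cost is one or two sentences and a small change to adverse event programming. Because the SAP is final at version 1.0, the change needs an amendment or a documented clarification before the tables are produced. Nothing changes in data collection or in how patients are dosed.

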#### Table 15.3.1.1 Overall Summary of TEAEs – Safety Set

An overview of TEAEs:

- TEAE
- Non-serious TEAE
- Serious TEAE
- TEAEs of special interest
- Related TEAE
- Related serious TEAE
- Mild TEAE
- Moderate TEAE
- Severe TEAE
- TEAE leading to down-titration
- TEAE leading to discontinuation
- Serious TEAE leading to discontinuation

- Related TEAE leading to discontinuation
- TEAE leading to death

will be displayed during the trial as well as the dose finding, maintenance, and down-titration periods by dose and overall for the patients in the safety set.

Table 15.3.1.2 Incidence of TEAEs – Safety Set

Table 15.3.1.3 Incidence of Serious TEAEs – Safety Set

Table 15.3.1.4 Incidence of TEAEs of Special Interest – Safety Set

Table 15.3.1.5 Incidence of Related TEAEs – Safety Set

Table 15.3.1.6 Incidence of Related Serious TEAEs – Safety Set

Table 15.3.1.7 Incidence of TEAEs Leading to Down-Titration – Safety Set

Table 15.3.1.8 Incidence of TEAEs Leading to Discontinuation – Safety Set

Table 15.3.1.9 Incidence of TEAEs Leading to Death – Safety Set

TEAEs occurring during the trial as well as the dose finding, maintenance, and down-titration periods will be summarised by concurrent dose and overall via the numbers of adverse events, as well as counts and percentages of patients having experienced adverse events during the dose finding and maintenance periods and overall. Percentages will be based on the number of patients in the safety set. Here and in the tables below the SOC and PTs within each SOC will be ordered by descending overall incidence.

In addition, the following will be provided summarised by SOC and PT for the safety set for each dose and overall:

Table 15.3.1.10 Incidence of TEAEs by Severity – Safety Set

Table 15.3.1.11 Incidence of TEAEs by Relationship to IMP – Safety Set

All adverse event data will be listed as follows:

Listing 16.2.4.1.1 Adverse Events: MedDRA Coding

Listing 16.2.4.1.2 Adverse Events: General – Enrolled Set

Listing 16.2.4.1.3 Non-Serious Adverse Events – Safety Set

Listing 16.2.4.1.4 Serious Adverse Events – Safety Set

Listing 16.2.4.1.5 TEAEs of Special Interest – Safety Set

Listing 16.2.4.1.6 AEs Leading to Discontinuation – Safety Set

Listing 16.2.4.1.7 AEs Leading to Death – Safety Set

All AEs will be displayed by patient including the PT of an AE, start and stop dates, duration and other characteristics of AEs.

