Duration of treatment for the individual patient: Maximum treatment duration will depend on the individual HTD. Patients tolerating Dose D (200 mg zamicastat) will take zamicastat for up to 124 days.

Test product, dose and mode of administration: Tablets for oral administration under fed conditions containing 100 mg of zamicastat (BIA 5-1058) each. It is planned to use the following doses:

- | | |
|--------|--|
| Dose A | 50 mg zamicastat once daily (half a tablet of 100 mg) |
| Dose B | 100 mg zamicastat once daily (one tablet of 100 mg) |
| Dose C | 150 mg zamicastat once daily (one and a half tablet of 100 mg) |
| Dose D | 200 mg zamicastat once daily (two tablets of 100 mg) |

Reference therapy, dose and mode of administration: NA

Criteria for evaluation:Primary endpoint; pharmacokinetics:

The following PK parameters (24-hour profile) for zamicastat and its metabolites will be derived after a single dose of 50 mg zamicastat at visit A1 (Day 1):

1. Area under the curve 0-24h (AUC_{0-24h})
2. Maximum plasma concentration (C_{max})
3. Time until C_{max} (t_{max})

The following PK parameters (24-hour profile) for zamicastat and its metabolites will be derived at steady-state at the individual HTD and will be taken at visit MPV3.

4. Area under the curve 0-24h ($AUC_{0-24h,SS}$)
5. Maximum plasma concentration ($C_{max,SS}$)
6. Time until $C_{max,SS}$ ($t_{max,SS}$)
7. Minimum plasma concentration at the end of the dosing interval ($C_{min,SS}$)

The following PK parameter (trough level) will be derived for each dose at steady-state.

8. Minimum plasma concentration at the end of the dosing interval ($C_{min,SS}$)

Additional PK parameters may also be calculated if considered appropriate.

Secondary endpoints:Safety and tolerability endpoints:

1. Adverse events
2. Clinically relevant changes in laboratory parameters (haematology, biochemistry, coagulation, urinalysis, arterial blood gas analysis)
3. Clinically relevant changes in vital signs
4. Clinically relevant changes in ECG
5. Number of digital scars (only in patients with scleroderma)
6. Skin score (only in patients with scleroderma)

Efficacy endpoints:

Change from baseline to MPV3 in:

7. PVR, right atrial pressure (RAP), mPAP, cardiac index (CI) and mixed venous oxygen saturation (SvO_2). Further haemodynamic parameters may also be calculated if considered appropriate.
8. 6-MWT, including Borg dyspnoea score
9. Biomarker (N-terminal pro brain natriuretic peptide [NT-proBNP])

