8. STUDY DESIGN

8.1 Overall Study Design and Plan

This is an open-label, multi-centre study in patients with PAH who are currently on stable treatment with at least one PAH medication. It is planned to evaluate the PK profile (24-hour profile and trough levels) and the safety, tolerability and efficacy of four different zamicastat doses. Each patient will start treatment with the lowest dose (50 mg zamicastat once daily) and the dose will be up-titrated to the individual highest tolerated dose (HTD) i.e. up to 200 mg zamicastat once daily.

A DSMB will periodically review the safety data and will issue a recommendation if the doses can be used as planned.

This study will consist of:

- A screening period, 5 to 12 days: visit V1
- Up to four dose finding periods, 14 days each:
 - Dose A: visits A1, A2 and A3
 - Dose B: visits B2 and B3
 - Dose C: visits C2 and C3
 - Dose D: visits D2 and D3
- Maintenance period, 42 days: visits MPV1, MPV2 and MPV3
- Follow-up period:
 - Visit FU (down-titration): 14 days after MPV3 (only for patients taking 150 mg or 200 mg zamicastat who will not participate in the extension study)
 - Visit FU: 14 days after last IMP intake

After confirmed eligibility, patients will initiate treatment with Dose A (50 mg zamicastat once daily) at visit A1 and will be treated with this dose level for 14 days. If Dose A was considered safe by the investigator, it will be up-titrated to Dose B (100 mg zamicastat once daily) at visit A3 and the patient will continue with this dosage for 14 days. Patients not tolerating Dose A have to be withdrawn from the study.

The up-titration is based on safety criteria, including but not limited to:

- Absence of symptomatic and/or clinically relevant orthostatic hypotension
- Systolic blood pressure (SBP) > 95 mmHg or diastolic blood pressure (DBP) > 50 mmHg
- Absence of clinically significant changes in ECG parameters (heart rate, P-R interval, QRS duration, QT and QTc interval)
- Absence of clinically significant hypersensitivity/skin allergic reactions

After a positive safety evaluation at visit B3, the dose will be up-titrated to Dose C (150 mg zamicastat once daily) and the patient will continue on this dose level for a further 14 days. If Dose C was tolerated by the patient, it will be up-titrated at visit C3 to Dose D (200 mg zamicastat once daily) where the patient will remain for 56 days (14 days dose finding period + 42 days maintenance period).

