10.3 Selection of Doses in the Study

10.3.1 Selection and timing of dose for each patient

Each patient will start treatment with 50 mg zamicastat once daily (Dose A) at visit A1 and will be up-titrated step by step to the individual HTD i.e. up to 200 mg zamicastat once daily. The 100 mg tablet has to be split at the break score in two equal halves using a pill splitter.

Table 2: Dosage regimen

	Daily dose
Dose A	50 mg (half a tablet of 100 mg)
Dose B	100 mg (one tablet of 100 mg)
Dose C	150 mg (one and a half tablet of 100 mg)
Dose D	200 mg (two tablets of 100 mg)

Each next dose will start after 14 days of treatment if the previous dose was considered safe by the investigator. The up-titration is based on the following safety criteria, including but not limited to:

- Absence of symptomatic and/or clinically relevant orthostatic hypotension
- SBP > 95 mmHg or DBP > 50 mmHg
- Absence of clinically significant changes in ECG parameters (heart rate, P-R interval, QRS duration, QT and QTc interval)
- Absence of clinically significant hypersensitivity/skin allergic reactions

Patients not fulfilling the criteria for up-titration after 14 days of treatment with 50 mg zamicastat have to be withdrawn from the trial.

If the patient's next dose will not be tolerated by the patient, the dose has to be down-titrated to his/her previous dose and this dose will be considered as the individual HTD, if tolerated by the patient. Treatment at the individual HTD will be for 42 days during the maintenance period.

Zamicastat has to be taken in the morning after breakfast. The patient must not take the tablet at home on visit days (A3/B3/C3/D3, MPV1, MPV2 and MPV3).

In case a patient missed to take the dose after breakfast, (s)he should take the dose after lunch. The next dose should be taken as scheduled. If the dose was missed after lunch too, the dose for this day has to be skipped.

Patients taking 150 mg or 200 mg of zamicastat and who will not participate in the extension study will take 100 mg zamicastat for 14 days.

In case a patient will discontinue the trial early due to the occurrence of an AE, down-titration is not mandatory, but at the investigator's discretion. In case down-titration is recommended by the investigator, it should follow the same procedure as described above.

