### 2.3 Overall Study Design

This is an open-label, multi-centre study in patients with PAH who are currently on stable treatment with at least one PAH medication. It is planned to evaluate the PK profile (24-hour profile and trough levels) and the safety, tolerability and efficacy of four different zamicastat doses. Each patient will start treatment with the lowest dose (50 mg zamicastat once daily) and the dose will be up-titrated to the individual **highest tolerated dose** (HTD) i.e. up to 200 mg zamicastat once daily.

A data safety monitoring board (DSMB) will periodically review the safety data and will issue a recommendation if the doses can be used as planned.

This study will consist of:

- A screening period, 5 to 12 days: visit V1
- Up to four dose finding periods, 14 days each:
  - o Dose A: visits A1, A2 and A3
  - o Dose B: visits B2 and B3
  - o Dose C: visits C2 and C3
  - o Dose D: visits D2 and D3
- Maintenance period, 42 days: visits MPV1, MPV2 and MPV3
- Follow-up period:
  - o Visit FU (down-titration): 14 days after MPV3 (only for patients taking 150 mg or 200 mg zamicastat who will not participate in the extension study)
  - o Visit FU: 14 days after last IMP intake

After confirmed eligibility, patients will initiate treatment with Dose A (50 mg zamicastat once daily) at visit A1 and will be treated with this dose level for 14 days. If Dose A was considered safe by the investigator, the patient will be up-titrated to Dose B (100 mg zamicastat once daily) at visit A3 and the patient will continue with this dosage for 14 days. Patients not tolerating Dose A have to be withdrawn from the study.

After a positive safety evaluation at visit B3, the patient will be up-titrated to Dose C (150 mg zamicastat once daily) and the patient will continue on this dose level for a further 14 days. If Dose C was tolerated by the patient, he/she will be up-titrated at visit C3 to Dose D (200 mg zamicastat once daily) where the patient will remain for 56 days (14 days dose finding period + 42 days maintenance period).

Patients not tolerating their next dose at any time during the 14-days dose finding period will come immediately to the site or call the investigator (unscheduled visit), unless intolerance was detected during a scheduled visit and the dose will be down-titrated to the patient's previous tolerated dose. Then they will continue this treatment for 42 days during the maintenance period.

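### The whole-trial by-dose TEAE columns, and Tables 15.3.1.10 and 15.3.1.11, pool 14 days at some doses with 56 at others without exposure adjustment, so a flat hazard can look like a dose gradient

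*SAP*

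**What the plan says.** **Attribution.** SAP 5.6.1: "Adverse events will be assigned to IMP dose groups based on the prescribed IMP dose at the date of AE onset". SAP 4.3 adds that patients are not put into separate dose groups for this purpose, so one patient can contribute to several dose columns.

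**Output.** TEAEs in Tables 15.3.1.2 to 15.3.1.9 "will be summarised by concurrent dose and overall via the numbers of adverse events", with counts and percentages of patients. The stated denominator is the safety set. The same sentence presents results for the whole trial and also for the dose finding, maintenance and down-titration periods. Table 15.3.1.1 has the same split. Tables 15.3.1.10 and 15.3.1.11 are introduced differently: "In addition, the following will be provided summarised by SOC and PT for the safety set for each dose and overall". No period is mentioned there.

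**Time at dose.** SAP 2.5: "Each next dose will start after 14 days of treatment if the previous dose was considered safe by the investigator". Protocol 8.1, on 200 mg: "where the patient will remain for 56 days (14 days dose finding period + 42 days maintenance period". Patients who step back to a lower dose stay on it (SAP 2.3): "Then they will continue this treatment for 42 days during the maintenance period". Protocol 10.3.1 says that patients on 150 or 200 mg who do not enter the extension study "will take 100 mg zamicastat for 14 days".

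**Exposure.** SAP 5.4.1 tabulates treatment duration by HTD and overall, not by concurrent dose. SAP 5.6.1 plans no person-time rate.

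**The concern.** A crude incidence rises with time at risk, and the titration design ties time at risk to dose. A whole-trial column for 200 mg can hold four times the observation per patient of a column for a dose that was only passed through. A lower dose that becomes the HTD also collects the 42 maintenance days, and 100 mg can collect taper days. Since exposure is tabulated by HTD only, the tables do not give the patient-days behind each dose column.

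Safety and tolerability of different doses is a secondary objective, and the primary objective is to find a promising dose range. There is no control arm and no randomised dose comparison, so readers are likely to use the by-dose TEAE columns for that purpose. A gradient produced by duration could then be read as an effect of dose, or could hide one.

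**Working it through.** **1. The plan's own durations.** At 200 mg: 14 + 42 = 56 days, as stated. The synopsis also says: "Patients tolerating Dose D (200 mg zamicastat) will take zamicastat for up to 124 days". Four steps, maintenance and taper give 4 × 14 + 42 + 14 = 112 days. Six visit windows of 2 days add 12, which gives 124. Nominal times are used below.

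**2. Flat hazard, every patient completing every step.** Let p be the 14-day risk of at least one TEAE. The documents give no value, so p is an assumption. The risk over d days is 1 − (1 − p)^(d/14), and 56/14 = 4.

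| p (14 days) | 56 days: 1 − (1 − p)^4 | Ratio |
|---|---|---|
| 5% | 18.5% | 3.7 |
| 10% | 34.4% | 3.4 |
| 20% | 59.0% | 3.0 |
| 30% | 76.0% | 2.5 |

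Expected event numbers differ 4-fold whatever p is.

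**3. Effect of the safety-set denominator.** Suppose that all patients spend 14 days at a lower dose and a share f spends 56 days at 200 mg, with nobody else exposed to 200 mg. The two percentages are equal when f = p / [1 − (1 − p)^4]. This is 0.05/0.185 = 27% for p = 5% and 0.30/0.760 = 40% for p = 30%. Below that share, 200 mg looks better than the lower dose.

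**4. Illustrative HTD mixes (assumptions).** Set p = 20%, let a failed step end at day 7, and let all completers enter the extension study. The shares for no HTD/50/100/150/200 mg are 3/6/8/8/75%, 5/10/15/20/50% and 5/20/25/25/25%. The risks are 10.6% over 7 days, 20.0% over 14 days and 59.0% over 56 days. Example, 200 mg in the last mix: 0.25 × 59.0% + 0.25 × 10.6% = 17.4% of the safety set. Half the patients are exposed to 200 mg, so this is 34.8% of those exposed.

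Whole-trial percentages at 50/100/150/200 mg:

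| HTD 200 mg | Safety-set denominator | Exposed denominator |
|---|---|---|
| 75% | 22.1/22.0/20.6/45.1 | 22.1/22.6/22.6/54.4 |
| 50% | 23.4/23.9/23.4/31.6 | 23.4/25.2/27.5/45.2 |
| 25% | 27.3/26.9/22.4/17.4 | 27.3/28.3/29.9/34.8 |

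The true hazard is the same at every dose in every row. If half the patients do not enter the extension study in the 75% mix, the taper raises the 100 mg safety-set figure from 22.0% to 28.6%.

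**5. Dose finding columns only.** With exposed patients as denominator, the 75% mix gives 19.7/19.4/19.2/19.1% and the 25% mix gives 19.5/18.0/16.9/15.3%. There is no upward gradient. The slight fall comes from steps cut short at day 7. With the safety set as denominator, the 25% mix gives 19.5/17.1/12.6/7.6%, so the denominator matters even here.

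**6. Rates.** First events per 100 patient-days are −100 × ln(1 − p)/14, which is 0.75 for p = 10% and 1.59 for p = 20%. Under a flat hazard this value is the same at every dose in every mix.

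**The case against.** The strongest reply is that the SAP already does most of the work. A reader might infer that no TEAE table takes account of time at dose. The documents do not support that, because Tables 15.3.1.1 to 15.3.1.9 are split by period. By SAP 4.6, dose finding ends the day before visit D3 or before down-titration, so each dose contributes at most one 14-day step. Maintenance is nominally 42 days at any HTD, and taper days have their own period. Much of the two unsplit tables is also available with the split: severity totals and related TEAEs in 15.3.1.1, and related TEAEs by system organ class and preferred term in 15.3.1.5. What lacks a split is mainly preferred terms by severity grade and by relationship category. All of this stands. It limits the point to the whole-trial columns and those two tables.

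A second reply concerns the remedy. A rate per patient-day assumes a roughly constant hazard. If events cluster just after a dose step, 42 stable days in patients selected for tolerance would dilute the rate at the HTD and make that dose look safer. Rates also leave selection and time since start in place. This stands too, and it is why the dose finding columns should remain the basis for comparing crude percentages.

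Third, the study is exploratory and descriptive, with about 32 patients and no between-dose test, and all AEs are listed. That lowers the stakes but does not make the pooled columns interpretable.

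**Conclusion.** The point holds for the whole-trial by-dose columns of Tables 15.3.1.1 to 15.3.1.9 and for Tables 15.3.1.10 and 15.3.1.11. These mix dose with duration, and no planned output adjusts for it. Under a flat hazard the spurious excess at 200 mg is about 3.7- to 3.0-fold for an assumed 14-day risk of 5% to 20%, provided that nearly all patients reach and complete 200 mg.

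A reader might go further and infer that 200 mg will necessarily look worse. The documents do not support this. They give no HTD distribution, and percentages use the whole safety set, so patients who never reach 200 mg dilute its figure. In the illustrative 25% mix the gradient reverses. The direction is therefore uncertain, but a gradient in either direction is an artefact when the hazard is flat.

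The hazards and HTD mixes are assumptions. The table shells are not in the documents, so the final column layout cannot be checked. This is an inexpensive reporting improvement, not a threat to the trial's primary objective.

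**What to change.** 1. Give Tables 15.3.1.10 and 15.3.1.11 the same period split as Tables 15.3.1.1 to 15.3.1.9.
2. In the whole-trial by-dose columns, add TEAE rates per 100 patient-days at each concurrent dose, with days summed by dose from the periods in SAP 4.6 and 5.4.1.
3. State to which dose, if any, a TEAE belongs when its onset falls in the 14 days after last intake. It counts as treatment-emergent, but no dose is then prescribed. The patient-days must follow the same rule.
4. Use patients exposed to that dose in that period as the by-dose denominator.
5. Tabulate treatment duration by concurrent dose as well as by HTD.
6. State that crude percentages are compared between doses only within the dose finding columns.

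The cost is SAP wording, shell changes, a new derivation of days per concurrent dose and one attribution rule. No new data are needed. The downside is that rates assume a roughly constant hazard and do not remove the selection of tolerant patients or the effect of time since start. A footnote should say so.
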